2.4 Secondary endpoints

Supportive secondary endpoints

Percentage of time spent in tight glycaemic target range (70-140 mg/dL (3.9-7.8 mmol/L), both inclusive is calculated in the same way as the primary endpoint using the relevant ranges. A sensitivity analysis using weights to account for heteroscedasticity due to a varying number of FGM readings will be performed as described previously.

Percentage of time spent in nocturnal glycaemic target range 70-140 mg/dL (3.9-7.8 mmol/L) both inclusive, in the nocturnal period (00:01 am–05:59 am both inclusive) will be calculated in the same way as the primary endpoint but only using readings with a time stamp in the relevant time period. A sensitivity analysis using weights to account for heteroscedasticity due to a varying number of FGM readings will be performed. As described previously the weights are calculated based on the total number of FGM readings and will in so doing not be adjusted to account for the lower number of nocturnal readings.

All the supportive secondary endpoints regarding time spent in target range are analysed and tested in the same model as the primary endpoint, i.e. one sided tests of the mean difference favouring IDeg must be statistically significantly different from zero at the 0.025 level to support superiority.

As stated in Section 9.1.1.4 of the protocol, sites are instructed not to initiate FGM monitoring periods that will contain daylight saving clock shifts. During data analysis it will be checked if this rule is obeyed, and the length of both the entire day in question in general, and the nocturnal period in question in particular will be adjusted equivalently when it is not. For example, if a subject is under FGM monitoring in the US on 11-MAR-2018 the nocturnal period will start at 00:01AM and end at 04:59 (nominal sensor time) instead of 05:59. In the data analysis one hour will be added to the recorded time points from 02:00 and onwards. In practise then, 11-MAR-2018 will consist of no more than 23h of FGM readings, and the nocturnal period of no more than 4h and 58 minutes of FGM readings. If on the other hand a subject is under FGM monitoring on 04-NOV-2018 in the US one hour will be deducted from the time recorded time points. This will then consist of no more than 25 hours of FGM readings, and the nocturnal period of no more than 6h and 58 minutes of FGM readings. The hour between 01:00-02:00 on 04-NOV will be represented twice in the data,

| Statistical Analysis Plan | | Date: | 23 January 2020 | Novo Nordisk |
|----------------------------|--------------|----------|-----------------|--------------|
| Trial ID: 1250-4419 | CONFIDENTIAL | Version: | 2.0 | |
| UTN: 1111-1203-0580 | CONFIDENTIAL | Status: | Final | |
| EudraCT no: 2017-004047-20 | | Page: | 10 of 17 | |

and to separate them an auxiliary variable stating if a time reading is in the daylight saving period or not will be added to all FGM readings.

The mean glucose levels (mmol/L) will be calculated as the mean of the FGM glucose levels and analysed by models and test equivalent to the primary endpoint. A sensitivity analysis using weights to account for heteroscedasticity due to a varying number of FGM readings will be performed as described previously.

FGM readings have a lower limit of quantification (LLOQ) of 40mg/dL or 2.2 mmol/L and a upper limit of quantification (ULOQ) 500 mg/dL or 27.8 mmol/L. LLOQ marked readings will be assigned the LLOQ value and ULOQ marked readings will be assigned the ULOQ value.

Mean HbA1c values will be analysed using a similar model as compared to the primary endpoint, but only a single two-sided test for statistically significant differences between IDeg and IGlar 100U/mL will be performed.

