10.3.2 Secondary endpoints

Supportive secondary endpoints

Percentage of time spent in tight glycaemic target range (70-140 mg/dL (3.9-7.8 mmol/L), both inclusive is calculated in the same way as the primary endpoint using the relevant ranges. A sensitivity analysis using the inverse of the square root of the number of FGM readings as inverse variance weights to account for heteroscedasticity due to a varying number of FGM readings will be performed.

Percentage of time spent in nocturnal glycaemic target range 70-140 mg/dL (3.9-7.8 mmol/L) both inclusive, in the nocturnal period (00:01 am–05:59 am both inclusive) will be calculated in the same way as the primary endpoint but only using readings with a time stamp in the relevant time period. A sensitivity analysis using the inverse of the square root of the number of FGM readings in the relevant time period as inverse variance weights to account for heteroscedasticity due to a varying number of FGM readings will be performed.

All the supportive secondary endpoints regarding time spent in target range are analysed and tested in the same model as the primary endpoint, i. e. one sided tests of the mean difference favouring IDeg must be statistically significantly different from zero at the 0.025 level to support superiority.

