2.2 Definition of analysis sets

The full analysis set is all subjects randomised at Visit 3. The safety analysis set is all subjects that are randomised and treated with at least one dose of trial drug after randomisation.

The PP analysis set consists of subjects that stay on assigned treatment until and complete FGM assessment at visits 21 and 39 respectively. Complete FGM assessment is specified as subjects having at least 70% of two weeks FGM measurements per maintenance period (2 * 960 measurements). FGM measurements from the first 24 hours of each fitted sensor are disregarded. All endpoint analysis will be performed on the PP analysis set.

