is smaller than 2.5%, where D is the estimated mean difference of time spent in glycaemic target range (IDeg OD - IGlar 100U/mL OD). As such, a fixed hierarchical testing procedure will be applied, which will effectively adjust for multiple testing.

Non-inferiority will be evaluated by comparing the lower limit of the two-sided 95% confidence interval for the difference between IDeg and IGlar 100U/mL to a non-inferiority margin of 0.2h/24h (0.83%). If the lower CI limit is above -0.83%, non-inferiority will be considered established. The two-tailed p-value will be reported for the test of superiority.

Missing data due to intercurrent events such as trial discontinuation is not relevant since the primary estimand is based on the PP analysis set.

A sensitivity analysis will be performed to account for heteroscedasticity due to a varying number of FGM readings within the 70% demand. Specifically, the primary endpoint will be analysed by applying the weight statement in the proc mixed procedure with weights calculated as the square root of the total number of FGM readings.

An additional sensitivity analysis will be performed where all subjects who have FGM readings for at least seven consecutive days will be included. Weighting will be performed as described previously.

Following specifications from the vendor the accuracy of the FGM measurements can be influenced by intake of either ascorbic or/and salicylic acid [1]. The level of consequence depends on the amount of the interfering substance active in the body [1]. Due to the trial design, doses of non-

| Statistical Analysis Plan | | Date: | 23 January 2020 | Novo Nordisk |
|----------------------------|--------------|----------|-----------------|--------------|
| Trial ID: 1250-4419 | CONFIDENTIAL | Version: | 2.0 | |
| UTN: 1111-1203-0580 | CONFIDENTIAL | Status: | Final | |
| EudraCT no: 2017-004047-20 | | Page: | 9 of 17 | |

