where N_FGM is the total number FGM readings in the relevant period. The number of hypoglycaemic episodes will be analysed using a negative binomial regression with treatment and period as fixed effects, subject as a normally distributed random effect and the log(PYE) as an offset. A p-value smaller than 0.025 for the one sided test of the rate ratio in favour of IDeg will be considered as support for superiority of IDeg over IGlar 100U/mL. If this model does not converge, a Poisson regression model will be fitted.

CONFIDENTIAL

Date: Version: Status: Page:

23 January 2020 2.0 Final 12 of 17 Novo Nordisk

3 Changes to the statistical analyses planned in the protocol

Updates to section 10 in protocol version 3.0 is described below.

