3.7 Further specification of weights for secondary endpoint (Percentage of time spent in nocturnal glycaemic target range)

p. 40 section 10.3.2:

"A sensitivity analysis using the inverse of the square root of the number of FGM readings in the relevant time period as inverse variance weights to account for heteroscedasticity due to a varying number of FGM readings will be performed."

Is replaced by:

"A sensitivity analysis using weights to account for heteroscedasticity due to a varying number of FGM readings will be performed. As described previously the weights are calculated based on the total number of FGM readings and will in so doing not be adjusted to account for the lower number of nocturnal readings."

Rationale: Due to the change in 3.3.

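### The nocturnal time-in-range sensitivity run is weighted by the 24-hour reading count, so it does not correct unequal variance that comes from night-specific missing readings

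*SAP*

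**What the plan says.** SAP 2.4 calculates nocturnal time in range like the primary endpoint, "but only using readings with a time stamp in the relevant time period". The purpose of the extra run is given in the same paragraph: "A sensitivity analysis using weights to account for heteroscedasticity due to a varying number of FGM readings will be performed". The weight comes from SAP 2.3, which uses the weight statement of the mixed-model procedure with "weights calculated as the square root of the total number of FGM readings". SAP 2.4 then states that the "weights are calculated based on the total number of FGM readings and will in so doing not be adjusted", and SAP 3.7 records the change in the same terms: the weights "will in so doing not be adjusted to account for the lower number of nocturnal readings".

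Three other places bear on this.

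- Protocol 10.3.2 specified, for this same run, the "inverse of the square root of the number of FGM readings in the relevant time period as inverse variance weights". The count was therefore restricted to the nocturnal window.
- SAP 3.7 justifies the replacement only by reference to SAP 3.3. SAP 3.3 replaces multiplication of the endpoint by a weight statement, so that full profiles count for more than partial ones.
- SAP 2.5, for nocturnal hypoglycaemic episodes, bases exposure on the night count, "where N_FGM is the total number FGM readings in the relevant period".

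The per-protocol minimum in SAP 2.2 (960 readings per maintenance period, that is ten full days) is a whole-day count.

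**The concern.** A weight that is meant to correct for reading density should follow the density of the readings behind the endpoint. Here the denominator of the endpoint is the night count and the weight is a function of the 24-hour count. A profile can be thin at night and nearly complete overall, or complete at night and thin by day. In the first case the weight stays close to full; in the second it is reduced although nothing is missing from the endpoint.

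SAP 3.3 does not require this. It changes how the weight enters the model, not which readings are counted. Its stated aim points the other way: for a night endpoint, a full profile is one with full night data.

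What is at stake is how the run can be read. If night readings are missing unevenly, agreement between the weighted and unweighted nocturnal results says little about robustness to that unevenness, because the weights hardly respond to it.

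**Working it through.** **Inputs.** One reading every 15 minutes (protocol 9.1.1.2). Complete profile after the first 24 hours are dropped: 13 × 24 × 4 = 1248 (SAP 2.3), which reproduces. Per-protocol minimum: 960 = 10 × 96 (SAP 2.2); exactly 70% of 1344 would be 940.8, so 960 is the ten-day rounding.

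**Night count.** At 15-minute spacing the window 00:01 to 05:59 holds 24 readings, or 23 if the stamps fall on the quarter hour (00:15 to 05:45). A full profile therefore has 13 × 24 = 312 night readings, or 13 × 23 = 299. The table uses 24.

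**Formulas.** Relative weight under the SAP = √(total/1248). Like-for-like comparator, keeping the SAP's square-root form but using the night count = √(night/312).

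**Range of the SAP weight.** From √(960/1248) = 0.877 to 1 for any per-protocol profile with 960 to 1248 readings.

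| Readings lost | Total | Night | SAP weight | √(night/312) |
|---|---|---|---|---|
| None | 1248 | 312 | 1.00 | 1.00 |
| 6 nights, days complete | 1248 − 144 = 1104 | 168 | √(1104/1248) = 0.94 | √(168/312) = 0.73 |
| 12 nights, days complete | 1248 − 288 = 960 | 24 | 0.88 | √(24/312) = 0.28 |
| 288 daytime readings, nights complete | 960 | 312 | 0.88 | 1.00 |
| 3 whole days of 13 | 960 | 240 | 0.88 | √(240/312) = 0.88 |

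With 23 readings per night the 6-night row becomes √(1110/1248) = 0.94 against √(161/299) = 0.73, and the 12-night row √(972/1248) = 0.88 against √(23/299) = 0.28. Nothing changes at two decimals.

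**Unequal variance left after weighting.** This step needs an assumption that is not in the documents: that the variance of nocturnal time in range is proportional to 1/(night count). The ratio to a full profile is then 312/night before weighting, and weight × 312/night after it; 1.00 means fully corrected.

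| Readings lost | Before | SAP weight | √(night count) |
|---|---|---|---|
| 6 nights | 312/168 = 1.86 | 1.75 | 1.36 |
| 12 nights | 312/24 = 13.0 | 11.4 | 3.6 |
| 288 daytime readings | 1.00 | 0.88 | 1.00 |
| 3 whole days | 312/240 = 1.30 | 1.14 | 1.14 |

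These are upper-end figures. Readings 15 minutes apart are correlated, and variation within a subject between nights and periods does not shrink in proportion to the reading count.

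**The case against.** The best defence is that the losses the documents foresee come in blocks. Sensors are dislodged (protocol 9.1.1.3) or removed before imaging or diathermy (9.1.1.4), and the first 24 hours of each fitted sensor are discarded (SAP 2.2). The sensor stores readings automatically and the reader stays at the site (9.1.1), so gaps do not depend on subjects scanning at night. Sites must also confirm 14 days of data before the switch or the end of treatment. A lower night count common to all profiles is a constant and leaves relative weights unchanged. When whole days are lost, the last row of each table shows that the total count does exactly as well as the night count in the same form.

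This stands, and it rules out a reading that a reader might infer: that the run cannot correct the unequal variance at all. It corrects as much as any square-root weight when losses are by whole days.

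The defence is not complete. Losses need not be whole days. As an illustration with assumed times, a sensor dislodged at 23:00 and replaced at a site visit at 09:00 excludes 10 + 24 = 34 hours, or 136 readings. These contain two full nights, 48 readings, so the night share of the loss is 48/136 = 35%, against 312/1248 = 25% in a full profile. The imbalance is modest, and the documents do not say how often larger night-only gaps occur. But the night count matches the total count under whole-day loss and follows the endpoint's own data otherwise, so nothing is gained by preferring the total.

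It is also fair to say that the choice is disclosed and logged in SAP 3.7. What is missing is a reason for it.

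**Conclusion.** The point holds in a limited form. The run does not correct unequal variance that comes from night-specific missing readings, and it down-weights profiles that lack only daytime readings. The size is 0.94 against 0.73 with 6 of 13 nights lost, and 0.88 against 0.28 (about 3.2-fold) in the extreme case of 12 lost. It is zero when whole days are lost. Where the trial falls between these depends on how gaps cluster by time of day.

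Two stronger readings are not supported.

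- A reader might set the extreme-case weight of 0.88 beside the remaining fraction of night readings, 24/312 = 0.08, and infer an 11-fold overweight. That compares a square-root weight with a linear fraction and assumes variance proportional to 1/(night count). Whether the weight should be the count or its square root is a separate question that affects every weighted run.
- A reader might infer that the nocturnal superiority result, the primary endpoint or the sample size is compromised. None of them uses this weight. The protocol names no confirmatory secondary endpoints, and no decision rule depends on the run.

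Severity is minor. The case for acting rests on an unexplained departure from the protocol and a negligible cost.

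**What to change.** In SAP 2.4 and 3.7, base the weight for this run on the number of nocturnal-window readings for that subject and period, after the first 24 hours of each fitted sensor are dropped. Keep the same form as the other weighted runs, so that only the count changes, and delete the statement that no adjustment is made. If the total count is to stay, SAP 3.7 should give a reason that SAP 3.3 does not supply.

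Do not add a minimum of 10 × 24 = 240 night readings to this run. With quarter-hour stamps, ten complete nights give 10 × 23 = 230, so a profile with ten complete days would meet the per-protocol rule and fail the minimum. An exclusion would also change the population, and a different result could then not be put down to the weighting.

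The cost is one sentence in two places and one variable in the program. SAP 2.5 already needs the night count for the exposure offset in the nocturnal episode analysis.

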2.5 Exploratory endpoints

Glycaemic variability will be calculated as the standard deviation (mmol/L) and coefficient of variation (%) of the FGM glucose levels during the 2-week maintenance treatment periods. Both will be analysed and tested with models and tests equivalent to the primary endpoint.

Mean insulin dose in international units is calculated as the mean dose over the maintenance treatment periods for each subject. It will be analysed and tested using models and tests equivalent to the primary endpoint.

Percentage of time spent in the hypoglycaemic alert range (54-69 mg/dL (3.0-3.8 mmol/l), both inclusive) and percentage of time spent in the clinically significant hypoglycaemic range (<54 mg/dL (<3.0 mmol/L)) are calculated in the same way as the primary endpoint using the relevant ranges. A sensitivity analysis using weights to account for heteroscedasticity due to a varying number of FGM readings will be performed as described previously.

All the exploratory endpoints regarding time in range are analysed and tested in the same model as the primary endpoint, i.e. one sided tests of the mean difference favouring IDeg must be statistically significantly different from zero at the 0.025 level to support superiority.

Number of hypoglycaemic episodes <54 mg/dL (<3.0 mmol/L) for at least 15 minutes and number of hypoglycaemic episodes <54 mg/dL (<3.0 mmol/L) for at least 15 minutes in the nocturnal period (00:01-05:59 AM, both inclusive) will be counted as follows: At least two consecutive FGM glucose readings (i.e., readings that follow each other continuously in time) in the specified range are counted as a hypoglycaemic episode. Two hypoglycaemic episodes must be separated by at least 15 minutes above the hypoglycaemic range, equivalent to 2 consecutive FGM readings above the relevant hypoglycaemic range to be counted as two or more episodes instead of one. For the

| Statistical Analysis Plan | | Date: | 23 January 2020 | Novo Nordisk |
|----------------------------|--------------|----------|-----------------|--------------|
| Trial ID: 1250-4419 | CONFIDENTIAL | Version: | 2.0 | |
| UTN: 1111-1203-0580 | CONFIDENTIAL | Status: | Final | |
| EudraCT no: 2017-004047-20 | | Page: | 11 of 17 | |

nocturnal episodes, only FGM readings in the relevant period will be used. Person years of exposure (PYE) will be calculated as

PYE=(N FGM*15 minutes)/(365.25 days/year*(24 hours)/day*(60 minutes)/hour)

where N_FGM is the total number FGM readings in the relevant period. The number of hypoglycaemic episodes will be analysed using a negative binomial regression with treatment and period as fixed effects, subject as a normally distributed random effect and the log(PYE) as an offset. A p-value smaller than 0.025 for the one sided test of the rate ratio in favour of IDeg will be considered as support for superiority of IDeg over IGlar 100U/mL. If this model does not converge, a Poisson regression model will be fitted.

CONFIDENTIAL

Date: Version: Status: Page:

23 January 2020 2.0 Final 12 of 17 Novo Nordisk

3 Changes to the statistical analyses planned in the protocol

Updates to section 10 in protocol version 3.0 is described below.

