2.1 Sample size determination

The sample size calculation is based on the primary objective for the primary estimand and the primary endpoint of the trial, and is performed as a paired-sample calculation in terms of the mean and standard deviation of the within pair difference within the PP using the paired t-test. Only one previous Novo Nordisk trial using CGM has had a similar design: NN1250-3874 comparing IDeg and IGlar 100U/mL in 24 T1DM subjects using a cross-over design. Regarding time in glycaemic target range (70-180 mg/dL) during the full 24 hours of the day, the within pair difference between IDeg and IGlar 100U/mL had a mean of 0.39 hours and a standard deviation of 2.3. Two previous Novo Nordisk studies have used CGM in T2DM subjects in parallel arm designs, NN1250-3579 and NN1250-3668. However, CGM technology used in those two T2DM trials is outdated compared to the devices used in the current trial, and they are therefore deemed irrelevant as to

| Statistical Analysis Plan | | Date: | 23 January 2020 | Novo Nordisk |
|----------------------------|--------------|----------|-----------------|--------------|
| Trial ID: 1250-4419 | CONFIDENTIAL | Version: | 2.0 | |
| UTN: 1111-1203-0580 | CONFIDENTIAL | Status: | Final | |
| EudraCT no: 2017-004047-20 | | Page: | 7 of 17 | |

guidance on expected difference between the two treatments in this trial. The results from the NN1250-3874 trial are used for sample size calculation despite the differences from the present trial, i.e. indication and length of maintenance treatment. A conservative standard deviation of 2.6 is used. To detect a mean difference of 0.39 with 85% power with a standard deviation of 2.6 based on a paired t-test and 1:1 randomisation requires 401 subjects included in the PP. See Table 3 for sample sizes based on a range of standard deviation and for mean differences of 0.39 and 0.5

| Effect | | | | |
|--------|------|------|--|--|
| SD | 0.39 | 0.50 | | |
| 2.0 | 239 | 146 | | |
| 2.3 | 315 | 192 | | |
| 2.6 | 401 | 245 | | |

Sample size is computed for 1:1 randomisation and 85% power. SD: standard deviation. respectively.

Table 1 Sample size and power for various standard deviations and effects

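### If the negative binomial model for the two exploratory episode counts fails to converge, the Poisson fallback makes no allowance for within-subject overdispersion, yet the one-sided 0.025 rule stays

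*SAP*

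**What the plan says.** SAP 2.5 defines two exploratory counts of episodes below 54 mg/dL, one over the whole day and one restricted to the night. Both are to be analysed by "negative binomial regression with treatment and period as fixed effects, subject as a normally distributed random effect and the log(PYE) as an offset". The decision rule follows: "A p-value smaller than 0.025 for the one sided test of the rate ratio in favour of IDeg" is taken as supporting superiority. The next and last sentence is "If this model does not converge, a Poisson regression model will be fitted".

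Nothing more is said about the fallback. No scale parameter, robust variance or separate decision rule is given, and the terms of the Poisson model are not listed. Protocol 10.3.3 has the same sentence, and SAP section 3, which lists the changes to Protocol section 10, leaves it alone. SAP 2.2 adds "All endpoint analysis will be performed on the PP analysis set", so each analysed subject contributes two periods.

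**The concern.** The planned model allows for two kinds of extra variation. The normal subject effect covers differences between subjects. The negative binomial dispersion covers variation beyond Poisson between one subject's two periods. In a cross-over the treatment contrast is made within subjects, so the second allowance is the one that determines its standard error. A plain Poisson model drops it, and keeping the subject effect does not put it back.

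Because 0.025 one-sided is the only rule stated, it carries over to the fallback by implication. In that case a statement that the data support superiority on either count could rest on a standard error that is too small. The time-in-range test and the non-inferiority/superiority sequence are not affected.

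**Working it through.** **Inputs from the documents.** Model, offset and one-sided 0.025: SAP 2.5. Two periods per subject: SAP 2.2. Number of subjects: 401, SAP 2.1.

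**The plan's own figure.** SAP 2.1: "To detect a mean difference of 0.39 with 85% power with a standard deviation of 2.6 based on a paired t-test". The noncentral t calculation (two-sided 0.05) gives 401, as stated. The normal approximation gives (1.960 + 1.036)² × (2.6/0.39)² = 8.978 × 44.44 = 399.0, rounded up to 400. So 401 is used below.

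**Assumed inputs.** The documents give no episode rate, dispersion or between-subject spread. Assumptions: mean μ of 0.2 to 2 episodes per subject-period, within-subject dispersion k of 0 to 1 (variance = mean + k × mean²), log-scale subject SD s of 0.8 to 1.0, exposure 90–100% of the window, no treatment effect.

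**Formula.** The true variance exceeds the Poisson variance by φ = 1 + k × E[μᵢ²]/E[μᵢ] = 1 + kμ·exp(s²) for a log-normal subject effect. The actual one-sided error is 1 − Φ(1.96/√φ).

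- k = 0: φ = 1 and the error is 2.5% whatever s is. Between-subject variation alone does no harm.
- μ = 1, k = 0.5, s = 1: φ = 1 + 0.5 × 2.718 = 2.36; 1.96/1.536 = 1.276; error 10.1%.
- μ = 2, k = 1, s = 1: φ = 1 + 2 × 2.718 = 6.44; 1.96/2.537 = 0.773; error 22.0%.

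**Simulation given that Poisson is fitted.** 5,000 replicates per setting; Monte Carlo SE about 0.2 percentage points at 2.5%. One-sided error in %:

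| μ | k | s | Poisson | Poisson conditional on subject | Subject-clustered sandwich | Single Pearson scale |
|---|---|---|---|---|---|---|
| 0.2 | 0 | 1.0 | 2.3 | 2.3 | 2.2 | 1.1 |
| 1 | 0 | 1.0 | 2.7 | 2.7 | 2.8 | 0.2 |
| 2 | 0 | 1.0 | 2.6 | 2.6 | 2.8 | 0.0 |
| 0.2 | 0.25 | 1.0 | 2.9 | 2.8 | 2.4 | 1.3 |
| 0.2 | 0.5 | 1.0 | 4.3 | 4.3 | 2.9 | 1.5 |
| 0.2 | 1 | 1.0 | 5.2 | 5.3 | 3.0 | 1.8 |
| 0.5 | 0.5 | 1.0 | 6.4 | 6.2 | 2.9 | 0.9 |
| 1 | 0.25 | 0.8 | 5.1 | 4.9 | 2.3 | 0.6 |
| 1 | 0.5 | 1.0 | 9.4 | 9.4 | 2.4 | 0.5 |
| 2 | 0.5 | 1.0 | 14.6 | 14.3 | 3.0 | 0.4 |
| 2 | 1 | 1.0 | 20.0 | 19.8 | 3.0 | 0.6 |

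The single Pearson scale factor is too conservative because it counts between-subject variation as error.

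**Does keeping the subject effect help?** At μ = 0.5, k = 1, s = 1, a random-intercept Poisson model gave 12% (300 runs), conditional Poisson 10% (4,000 runs) and plain Poisson 9.6% (10,000 runs). It does not help.

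**When is the fallback reached?** The planned model was fitted by 15-point quadrature. The count is of datasets with dispersion below 0.005, subject SD below 0.02, or a singular Hessian:

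| μ, k, s | Share |
|---|---|
| 1, 0.5, 1.0 | 0/1500 |
| 0.2, 1, 1.0 | 55/1500 |
| 0.2, 0.5, 1.0 | 154/1500 |
| 0.1, 1, 1.5 | 247/1500 |
| 0.05, 1, 1.5 | 570/1497 |
| 1, 0, 1.0 | 908/1500 |

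With Poisson used only in those datasets, overall error is 1.8–3.0%. Within them it is 2.1–5.7% for Poisson and 2.4–5.7% for the sandwich (small subsets, SE up to about 3 points).

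**Numerical failure.** A rough pseudo-likelihood fit capped at 20 iterations, with 25 datasets per setting, failed to converge in 5 of 25 at μ = 1, k = 0.5 and in 25 of 25 at μ = 2, k = 1. This shows that the fallback can be reached in overdispersed data. It does not estimate how often production software would fail.

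**The case against.** The strongest reply is that the large figures describe a situation the plan would rarely enter. Poisson is used only after the negative binomial fit fails. Failure through a variance estimated at zero is common when there is no overdispersion, where Poisson is adequate, and almost absent when overdispersion is large: 0/1500 at μ = 1, k = 0.5, and in a smaller check 0/200 at μ = 2 with k = 0.5 or 1. Under that route the overall error is 1.8–3.0%, and the sandwich shows no gain in the failed datasets. This stands, and it means that 20% must not be read as the error rate of the planned procedure. It does not cover failures from starting values, quadrature or iteration limits. Those were not part of the quadrature simulation, and the rough fit shows that they can occur in overdispersed data.

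It can also be said that the fallback sentence follows the full model statement, so the natural reading changes only the distribution and keeps the other terms. That is a fair reading, but the inflation is nearly the same either way.

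Finally, the counts are exploratory, and many other endpoints are tested at the same level without multiplicity control, so no familywise error rate depends on them. This also stands and limits the severity.

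**Conclusion.** The concern holds, as a minor point. The fallback omits the within-subject overdispersion that the planned model allows for, and keeps the same threshold. Given that Poisson is fitted, one-sided error is 2.3–2.7% without such variation and 2.9–20.0% with it, over the assumed settings above. If the fallback is entered only through a zero variance estimate or a singular Hessian, overall error is close to nominal at 1.8–3.0%. The remaining risk comes from numerical failure, whose probability cannot be derived from the documents. Confidence is medium, because the rates, dispersion and convergence behaviour are all assumed and the optimiser used here is not SAS. Only the two exploratory episode counts are affected.

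**What to change.** Replace the fallback sentence in SAP 2.5 and record the change against Protocol 10.3.3 in SAP section 3. Suggested wording:

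> Should the negative binomial model fail to converge, a marginal log-linear (Poisson) model will be fitted with treatment and period as fixed effects, log(PYE) as offset and a robust (sandwich) variance clustered on subject.

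The report should state which model was used for each count. A single Pearson scale factor is not a good substitute (0.0–1.8% in the table).

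The cost is one sentence and one standard procedure option. Where Poisson is adequate, the error is 2.2–2.8% against 2.3–2.7%; power was not computed. There are two downsides. The rate ratio becomes marginal rather than subject-specific, which matters little because with a log link and a random intercept the treatment rate ratio is the same quantity. The robust test can also run at about 3–4% with very skewed counts: further simulations over other assumed settings reached 3.6% and 4.0%.
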